Screening/baseline/interview	30/20/50
Mid-treatment	50
Posttreatment	75
3-month follow-up	85
6-month follow-up	100

B. Treatment

1. Assignment

Participants will be randomly assigned to treatment following the completion of baseline assessment measures that establish their eligibility for the trial.

2. Delivery

Both study treatments, which are summarized in **Section V**, will be delivered according to standardized manuals. We will use the manuals and the therapist and patient materials developed for the PE and CPT rollouts to administer the treatments. The manual for each treatment is provided in Volume 2 of the study protocol. Treatment will be delivered in an outpatient setting.

PE and CPT will be administered approximately weekly, although sessions may be held more or less frequently than once a week if needed, e.g., to accommodate a patient's scheduling needs or to help a patient finish treatment within 20 weeks. For the sake of brevity, session frequency is described as "weekly" throughout this protocol. The standard protocol for PE is 8-15 sessions (10 sessions were used for PE in CSP #494), whereas the standard protocol for CPT is 12. Given the flexibility in the number of sessions allowed according to the protocols in the VA rollouts, it would be difficult to constrain the total number of sessions to 12 in CPT and 10 in PE. Therefore, we propose to administer 12 sessions of each treatment as a standard "dose" but to allow participants who improve more rapidly to finish in 10 or 11 sessions and participants who have not attained adequate improvement by session 12 to have up to 2 additional sessions.

Data from the rollouts suggests that this range will address the needs of most Veterans who participate in the trial (**Table VIII.3**). The average number of sessions among treatment completers is 11-12. There are not fixed criteria for determining completion in either rollout, however. In PE, completion is defined as attending at least 8 sessions. In CPT, completion is

based on improvement as determined by clinical judgment and decrease in PCL scores, which is more comparable to what we propose to use.

	Ν	Mean (SD)	< 10	10-14	> 14	
Prolonged Exposure	1,723	11.09 (2.62)	28.9%	59.7%	11.4%	
Cognitive Processing Therapy	689	11.83 (1.88)	8.1%	87.0%	4.9%	

Table VIII.3. Number of Sessions in Veterans Completing Treatment in the VA Rollouts

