CSP #591, version 11.0, February 16, 2018 44 Therefore, in addition to reporting number of sessions attended in each condition, we will also examine variability in early versus late completion in PE and CPT and explore how the variables relate to outcomes.

There are no standardized criteria for determining number of sessions for completion in the rollouts, so we are proposing procedures based on experience in the rollouts as well as studies that have used flexible dosing of manualized protocols for treating PTSD ([name] et al., 2005; Galovski et al., 2012; Levitt et al., 2007). Our aim is to optimize standardization and flexibility by ensuring that participants achieve substantial gains before terminating early (to ensure that they are stably improved) and at the same time not requiring extra sessions unless participants have failed to achieve an adequate response.

Participants who have experienced stable remission before completing 12 sessions many terminate early. Stable remission will be defined as 2 consecutive sessions in which the study participant reports (the DSM-5 equivalent of) a PCL score below 29 according to DSM-IV criteria. Beginning at session 8, participants who have a PCL below 29 for 2 consecutive sessions may terminate treatment early and receive the final session content at the subsequent session if they prefer to not complete all 12 sessions (i.e., in session 10 for someone remitted in sessions 8 and 9 and session 11 for someone remitted in sessions 9 and 10). A score of 29 was chosen because it is the lowest possible score on the PCL that could meet the DSM-IV symptom criteria for PTSD, and also corresponds to the definition of remission as a score below 20 on the CAPS (Weathers et al., 2001).

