5. Exploratory analyses

We will explore potential heterogeneities of treatment effect in the primary outcome by performing tests of treatment by subgroup interaction and by displaying treatment effects with their 95% confidence estimates within subgroups. The purpose of these exploratory analyses is to detect apparent reversals of effect or major quantitative interactions, in order to describe the uniformity or variation of effect appropriately. One major subgroup analysis concerns the sex of the participant. By enlisting the help of PBRN, we will try to recruit sites with large pools of female PTSD patients in this study; however, despite our efforts, it is not expected that we will be able to recruit a sufficient number of females to provide more than a preliminary idea of the effect in that subgroup. Other major subgroups will be era, age, race/ethnicity, MST, TBI, comorbid depression, and comorbid substance abuse. Because of the exploratory nature of these analyses, we do not plan to adjust for multiple comparisons.

We will also compare the following variables between PE and CPT: (1) the proportions of study participants meeting the stable remission criterion [early (<12 weeks), on time (12 weeks), late (>12 weeks), did not reach remission], by Chi-square tests; (2) the number of weeks to reach the stable remission criterion, by logrank tests; and (3) the number of sessions and total number of hours delivered, by two-sample t-tests. Mixed effects models or generalized estimating equations may be used to incorporate correlations due to therapists or to explore site variation. Interpretation of these results will incorporate early withdrawal of study treatment, early withdrawal of study, and initiation of non-study treatment for PTSD. We will also examine whether and how treatment dose (such as number of sessions and total number of hours), treatment engagement (homework) and treatment fidelity (therapist adherence and competence) relate to primary and secondary outcomes within and between treatments, and whether and how time to stable remission (such as early vs. on time vs. late) relates to outcomes within and between treatments.

E. Interim Analysis

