We will explore potential heterogeneities of treatment effect in the primary outcome by performing tests of treatment by subgroup interaction and by displaying treatment effects with their 95% confidence estimates within subgroups. The purpose of these exploratory analyses is to detect apparent reversals of effect or major quantitative interactions, in order to describe the uniformity or variation of effect appropriately. One major subgroup analysis concerns the sex of the participant. By enlisting the help of PBRN, we will try to recruit sites with large pools of female PTSD patients in this study; however, despite our efforts, it is not expected that we will be able to recruit a sufficient number of females to provide more than a preliminary idea of the effect in that subgroup. Other major subgroups will be era, age, race/ethnicity, MST, TBI, comorbid depression, and comorbid substance abuse. Because of the exploratory nature of these analyses, we do not plan to adjust for multiple comparisons.

We will also compare the following variables between PE and CPT: (1) the proportions of study participants meeting the stable remission criterion [early (<12 weeks), on time (12 weeks), late (>12 weeks), did not reach remission], by Chi-square tests; (2) the number of weeks to reach the stable remission criterion, by logrank tests; and (3) the number of sessions and total number of hours delivered, by two-sample t-tests. Mixed effects models or generalized estimating equations may be used to incorporate correlations due to therapists or to explore site variation. Interpretation of these results will incorporate early withdrawal of study treatment, early withdrawal of study, and initiation of non-study treatment for PTSD. We will also examine whether and how treatment dose (such as number of sessions and total number of hours), treatment engagement (homework) and treatment fidelity (therapist adherence and competence) relate to primary and secondary outcomes within and between treatments, and whether and how time to stable remission (such as early vs. on time vs. late) relates to outcomes within and between treatments.

I. Presentation of results

Interim reports will be presented in tables and graphs.

J. Visit windows

Table II.2: Visit Windows

Visit	Range
Phase 1 Screening	No range for phase 1
Phase 2 Screening	0-30 days after phase 1
Phase 3 Screening	0-30 days after phase 2
Randomization	0-7 days after phase 3

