Treatment Session 1	0-30 days after randomization
Treatment Session 2-14*	7-21 days after previous session
Mid-Treatment Assessment (Session 6)	0-14 days after session 6
Post Treatment Assessment	0-14 days after final treatment session
3-month Assessment	3 months ±2 weeks after final treatment session
6-month Assessment	6 months ±2 weeks after final treatment session

* The site SC and therapist will make sure Treatment Session 7 is scheduled after the "Mid-Treatment Assessment (session 6)" visit.

K. Rules for handling windows with more than one visit

Visit follows sequentially from previous visit. Thus, it won't be an issue for this study. If a visit is late in the follow-up phase, the late visit will be assigned to the visit with the closest target date.

L. Data inclusion/exclusion decision rules

Plan to use the data from all randomized participants in the analyses, regardless of the number of sessions they have completed. However, for sites with questionable data the study Executive Committee and Data Monitoring Committee will make recommendation to CSR&D Director whether to exclude the data from analyses or not.

M. Definition of compliance

Treatment compliance and termination will be reported and monitored. Regardless of their treatment compliance levels, the data from all participants will be used for analyses.

N. Methods for handling multiple observations

Appropriate methods for analyzing repeated measures data (e.g., mixed effects models, generalized estimating equations) as described in Sections II.H.2 and II.H.3 above.

- O. Use of baseline variables See Section II.H.1 above.
- P. Rules for calculation of derived variables See Section II.H.2 above.
- Q. Use of covariate data See Sections II.H.4 and II.H.5 above.
- R. Rules for stopping the trial, and allowance for them in the analysis See Section II.D.2 above.

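### Stable remission is defined by sessions but classed and timed in weeks with no stated start, and therapist adjustment of these exploratory comparisons is left optional

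*SAP*

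**What the plan says.** Protocol VIII.B.3 builds the criterion from session scores: "Stable remission will be defined as 2 consecutive sessions in which the study participant reports (the DSM-5 equivalent of) a PCL score below 29". Early completion is also counted in sessions: the final content is given "in session 10 for someone remitted in sessions 8 and 9 and session 11 for someone remitted in sessions 9 and 10". The standard course is 12 sessions, with up to 2 more for participants who have not improved enough.

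SAP II.H.5 and Protocol X.D.5 change the unit. They compare the arms on the classes "early (<12 weeks), on time (12 weeks), late (>12 weeks), did not reach remission" by chi-square, and on "the number of weeks to reach the stable remission criterion, by logrank tests". They compare sessions and hours delivered by two-sample t-tests. The timing classes are then used again to relate time to remission to outcomes. Neither text says whether the weeks run from randomization or from session 1.

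On spacing, Protocol VIII.B.2 says that "sessions may be held more or less frequently than once a week if needed", Protocol VIII.B.3 aims for completion within 20 weeks, and SAP II.J (Table II.2) sets the window for sessions 2 to 14 at "7-21 days after previous session". Session 1 may take place up to 30 days after randomization.

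On clustering, the sentence after the named tests reads: "Mixed effects models or generalized estimating equations may be used to incorporate correlations due to therapists".

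**The concern.** Twelve sessions and twelve weeks are the same thing only under particular assumptions about spacing and clock start. Where they differ, the classes mix speed of response with appointment scheduling. That matters most if spacing differs by arm. PE sessions last 90 minutes and CPT sessions one hour, and Protocol I.C.4 notes that the CPT length fits VA scheduling more easily. If PE visits were spaced further apart for that reason, a comparison in weeks would favour CPT even with equal response per session. The documents give no spacing data, so this is a risk and not a finding. Because the classes are reused as a predictor of outcome, any ambiguity carries forward.

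The second issue is the tests. Protocol X.B.3 expects participants of one therapist to be correlated, and each therapist delivers only one treatment, so the correlation bears fully on the comparison between arms. With adjustment optional and not tied to any test, the choice can be made after both results are known. No clustered counterpart of the log-rank test is named.

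**Working it through.** **The plan's own clustering figure.** Inputs from Protocol X.B.2 and X.B.3: therapist variance 36, within-subject variance 174, three post-treatment assessments, difference 5, two-sided 5% level, 90% power, m = 8.

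- Variance of the outcome: 36 + 174/3 + 174 = 268, so τ = 16.4.
- Per group before inflation: 2 × (1.960 + 1.282)² × 268/25, rounded up to 226 (452 in total).
- ρ = 36/268 = 0.134; f = 1 + 7 × 0.134 = 1.94.
- 226 × 1.94, rounded up, is 439 per group, or 878. This matches Table X.1.

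**Sessions against weeks.** Counted from session 1, session s falls (s − 1) × mean spacing days later, and 12 weeks is 84 days. The spacing at which session s passes 12 weeks is therefore 84/(s − 1).

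| Criterion first met at session | Weeks at 7-day spacing | Weeks at 21-day spacing | Later than 12 weeks if mean spacing exceeds |
|---|---|---|---|
| 5 | 4 | 12 | 21.0 days |
| 9 | 8 | 24 | 10.5 days |
| 10 | 9 | 27 | 9.3 days |
| 11 | 10 | 30 | 8.4 days |
| 12 | 11 | 33 | 7.6 days |

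- *Slow pace.* Twelve sessions spread over the full 20 weeks are 140/11 = 12.7 days apart. Session 9 then falls at 14.5 weeks and session 10 at 16.4 weeks: late by weeks, early by sessions.
- *Exact weekly pace, clock from session 1.* Session 12 falls at week 11 and is early. Session 13, an additional session, falls at week 12 and is on time.
- *Exact weekly pace, clock from randomization.* With session 1 at day 30, session 9 falls at day 30 + 56 = 86 and is late.
- *Faster than weekly,* which Protocol VIII.B.2 allows. At 6-day spacing, session 14 falls at 13 × 6 = 78 days, or 11.1 weeks: early by weeks, late by sessions.

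**Size of an unadjusted test.** Size = 2 × [1 − Φ(1.96/√f)], with f = 1 + 7ρ. The documents give no therapist correlation for remission timing, sessions or hours, so every ρ below is an assumption; 0.134 is borrowed from CAPS change.

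| ρ | f | True size of a nominal 5% test |
|---|---|---|
| 0.02 | 1.14 | 6.6% |
| 0.05 | 1.35 | 9.2% |
| 0.10 | 1.70 | 13.3% |
| 0.134 | 1.94 | 15.9% |
| 0.15 | 2.05 | 17.1% |

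**The case against.** The strongest reply is that the weeks may be sessions under another name. Protocol VIII.B.2 says it uses weekly as shorthand for session frequency, and the PCL, given at each session, is listed as weekly in Protocol Table VIII.1 and SAP Tables I.1 and II.1. The sentence allowing other frequencies entered VIII.B.2 with protocol version 10.0 in October 2017, after the SAP of April 2014. This stands as a plausible reading, but the SAP does not state it, and the SAP's own visit windows already allowed gaps of up to 21 days. If sessions were meant, the text should say so.

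A reader might infer that anyone who finishes early in sessions is counted as late. The documents do not support that. At weekly spacing, remission at session 9 or 10 is early on both scales. The criterion also has no minimum session: session 8 limits only the option to stop early. Someone below the threshold at sessions 4 and 5 meets the criterion at session 5, and counted from session 1 no permitted spacing puts that beyond 12 weeks. The 10.5-day limit applies only to a participant who first meets the criterion at session 9.

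A reader might also infer that the plan ignores clustering, or that its p-values will certainly be too small. The same paragraph does provide for mixed models or GEE, so the fair criticism is that adjustment is optional and not assigned to each test. For hours delivered, type I error matters little, because the session lengths build in a difference.

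Two more points stand. Calendar time to remission is a legitimate quantity in a comparative effectiveness trial, so weeks should be kept. And session counts are already to be compared and related to outcome, though not as the time scale for remission.

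**Conclusion.** The point holds as a minor one. The criterion and the classes use different units, the clock start is missing, and the two scales can disagree in either direction within the spacing that the documents allow. Some labels shift even at exact weekly pace, depending on the start chosen. How many participants are affected is unknown, because no distribution of session spacing is given.

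The named tests do not model therapist clustering, which the plan itself expects. The possible effect on a nominal 5% test runs from about 7% to 13% for correlations of 0.02 to 0.10, and about 16% if the CAPS-change value applied. These are illustrations with 8 participants per therapist, not estimates for these outcomes.

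All of this concerns exploratory analyses without multiplicity adjustment. The primary model includes a therapist random effect and does not use the remission classes, so no primary conclusion changes.

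**What to change.** In SAP II.H.5, and in the matching text of Protocol X.D.5:

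1. Define the classes by the session at which the criterion is met: early before session 12, on time at session 12, late after session 12, not reached. Use session number as the main time scale for the time-to-remission comparison.
2. Keep weeks as a secondary description, with the clock start stated.
3. Make therapist-adjusted methods the stated analysis: a mixed model or GEE for the classes and for sessions and hours, and a clustered or frailty time-to-event model in place of the plain log-rank test. Report the unadjusted tests as description.

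This changes analysis definitions only and leaves the treatment-completion rules alone. No new data are needed: the PCL is given at each session and sessions attended are already to be reported. The cost is an amendment under Protocol X.G, a little more analysis work and slightly wider intervals.
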